1.0 Introduction

Tampax tampons have been used for over 80 years as an internal method of absorbing menstrual flow. Tampons are constructed of 100% cotton, 100% rayon, or blends of cotton and rayon. They are manufactured with or without an overwrap and may be provided with a cardboard or plastic applicator for inserting the tampon into the vagina.

The study involves normal menstrual use. Prior experience has indicated that the study design described below effectively detects any differences between test products with a long history of safe (as labeled) use. In addition, a questionnaire completed by the subjects, after product use, has been found to be a sensitive way of detecting any product-related sensations such as burning, stinging, irritation and comfort.

2.0 Study Objectives

2.1 Objective(s)

1. The objective of this study is to support a claim of “clinically tested” while women wear tampon(s) during their full menstrual period with medical and gynaecological assessments of vaginal health and consumer self-reported assessments of comfort.
2. To confirm the tolerability of four (4) tampon products based on a body of evidence associated with multiple assessments of vaginal health and adverse events. The primary conclusion will be derived from the clinical assessments including vaginal erythema, ulcerations, abrasions, vaginal pH, vaginal discharge, and Adverse Events (AEs).
3. Usage diaries and questionnaires are added for learning purposes regards to comfort and tolerability.

3.0 Investigational Plan

3.1 Study Design

This will be a 4-consecutive menstrual cycle, single center, randomized, controlled, double-blind, crossover study conducted with approximately 100 menstruating women to complete with 65. Women aged **18-55** who report having consistent menstrual cycles and who typically use tampons as their main source of feminine protection during their menstrual cycles. Each subject will test each of the four (4) tampon products, testing one (1) product per monthly menstrual cycle over the course of this study. The order of the products tested will be randomized for each subject. Subjects will be given a tampon use diary to be completed after the use of each tampon and a Monthly Comfort Questionnaire to be completed at the end of each menstrual cycle.

Subjects will be instructed to call after the start of each period and schedule their gynecological examination visit **within 72** hours after the use of their last tampon for each period. Women who choose to use a backup menstrual protection product in addition to their assigned test tampon, will be provided currently marketed Always Ultrathin, Always Pantiliners and Always Overnight pads in the product’s marketed packaging. Subjects will be given instructions, including to refrain from using any douche products, sexual lubricant (except lubricated condoms), vaginal medications, suppositories, feminine deodorant spray, powder (in the perineal area), or vaginal wipes at least 48 hours prior to the screening visit and for the duration of their study

participation. Subjects will be given instructions to refrain from sexual activity for at least 48 hours prior to every gynecological examination visit. Subjects will be asked to refrain from bathing and use of antibacterial soaps while on the study, and from any vaginal hair removal 12 hours prior to the screening visit. During the tampon use phase of the study, subjects will be queried for changes in their health and medications at every visit. If during their monthly gynecological examination, a vaginal or pelvic organ associated adverse event is reported or found, if the subject wishes to continue in the study, the PI will make the continuance decision on a case by case basis after consultation with the Sponsor.

3.2 Selection of Study Population

3.2.1 Inclusion Criteria

To be considered eligible for enrollment into this study subjects must meet the following criteria:

- 1) signed the Informed Consent;
- 2) female, between 18 and **55** years of age;
- 3) agree to practice abstinence or use an effective form of birth control (e.g. intrauterine device, oral contraceptives, contraceptive implants or injections, diaphragm with spermicide, cervical cap, or constant use of condom) for at least the past 4 months and willing to continue throughout the study or have had a tubal ligation or your partner has had a vasectomy at least 4 months before being enrolled in the study;
- 4) be in generally good health without clinically significant disease as determined by investigator or designee based on medical history and vaginal exam;
- 5) for at least the last 4 months, have a consistent menstrual cycle lasting 21-35 days with menstrual bleeding lasting at least 3 days' duration;
- 6) primarily use tampons for their feminine protection needs during their periods (may use provided pads and/or pantiliners as back-up to tampon);
- 7) typically use Regular (6-9 grams) absorbency tampons for the majority of their period;
- 8) wears tampons during menstruation with no history of abnormal discomfort;
- 9) last pap smear was normal in the past 3 years or a normal pap with a negative HPV in the past 5 years (age 18-21 does NOT need a PAP if they have never been sexually active), per standard of care (per ACOG guidelines), (self-reported);
- 10) agree to refrain from vaginal intercourse within 48 hours of each vaginal exam scheduled visit;
- 11) agree to refrain from showering within twelve (12) hours or bathing within twenty-four (24) hours (1 day) of each visit (except Visit 2);
- 12) agree to refrain from using douching substances, feminine hygiene products, and to not apply powders, perfumes, wipes, lotions, creams, or emollients to their genital area 48 hours prior to **the screening visit and through the completion of the study, if accepted to participate in the study;**
- 13) agree to refrain from taking anti-inflammatory, antihistamine and/or, steroid systemic and/or topical, (including new hormonal contraceptives) medications until they have completed the study (e.g. Advil, Motrin, Benadryl, etc.);
- 14) agree to only use the tampons, pads and pantiliners supplied at each study visit for her menstrual protection while participating in this study;
- 15) be willing and able to comply with the study requirements;

- 16) agree to complete all study questionnaires;
- 17) agree to refrain from participation in other concurrent clinical research studies;
- 18) agree to refrain from genital hair removal (e.g. waxing/shaving, etc.) while on the study;
- 19) agree to refrain from using antibacterial body soap while on the study (e.g. safe guard)

3.2.2 Exclusion Criteria

Subjects will be excluded from the study if they meet any of the following criteria:

- 1) have a menstrual abnormality within the last 4 months (such as oligomenorrhea or amenorrhea);
- 2) has had a vaginal delivery in the last 6 months;
- 3) had vaginal surgery, perineal surgery, uterine surgery, miscarriage or abortion in the last 6 months;
- 4) are pregnant (per urine pregnancy test at screening), or intend to become pregnant in the next 5 months;
- 5) have a history of Toxic Shock Syndrome (TSS);
- 6) have a history of heart valve replacement;
- 7) have had an abnormal Pap in either of your last 2 Pap Smears;
- 8) have taken steroids (systemic and/or topical), corticosteroids, antihistamines, and/or anti-inflammatories within the past seven days (excludes hormonal contraception);
- 9) have a history of immunosuppressive drug therapy, chemotherapy, or radiation therapy;
- 10) have uncontrolled and/or unstable diabetes (*exception...stable dose of Diabetic medication for at least 6 months prior to enrollment*) in the opinion of the Investigator;
- 11) have a vulvar piercing;
- 12) have a history of genital herpes;
- 13) within the last 6 months have had endometrial disease/uterine fibroids with symptoms of heavy menstrual flow (super plus tampon absorbency use) and/or severe menstrual cramping;
- 14) have you been diagnosed with a current medical condition which might compromise the immune system functions; including cancer, anemia, leukopenia, leukocyte function deficiency, malnutrition, or chemical dependence (e.g. opiates, marijuana etc.) (self-reported);
- 15) have clinically diagnosed genital warts, lesions, and/or vaginal infections (such as bacterial vaginosis (BV), *Candida spp.*, *Trichomonas vaginalis*) at the screening visit;
- 16) have clinically diagnosed active or vaginal infections (*Chlamydia trachomatis* and/or *Neisseria gonorrhoeae*) identified through lab results from the microbiological sample obtained at the screening visit;
- 17) has urinary incontinence which causes subject to regularly use and saturate diapers or absorbent panties or pads more than 3 times a week over the last 4 months, or currently under treatment for a pelvic floor disorder (*i.e.*, perineal floor re-education with vaginal probe within last 6 months);
- 18) have history of or current diagnosis of AIDS/HIV, organ transplant, neoplasia, liver disease, renal disease, deep vein thrombosis, pulmonary embolism, haemophilia, neutropenia, autoimmune disease, major depression or any other medical condition,

which in the opinion of the Investigator would preclude study participation (*exception...stable dose of Thyroid medication for at least 6 months prior to enrollment*);

- 19) currently using a vaginal probiotic therapy (self-reported);
- 20) have participated in a clinical study with exposure to any investigational drug product within 30 days prior to this study;
- 21) have a vaginal erythema grade of ≥ 2.0 and/or the presence of abrasions and/or ulcerations as determined by investigator, at the screening visit;
- 22) have taken antibiotics or antifungals within last 4 weeks (Topical use of antibiotics or antifungals outside the perineal/genitourinary area is allowed at the discretion of the Investigator);
- 23) have started a new hormonal birth control in the previous 4 months or plan changing hormonal birth control throughout the study period;
- 24) currently experiencing bladder, uterine or rectal prolapse (investigator to verify at screening visit).
- 25) history of led or laser vaginal therapy within last 6 months (self-reported).

3.2.3 Continuance Criteria

Subjects will be excluded from the study if they meet any of the following criteria, and that, as determined by the investigator, would unduly influence the study or the participant's health with their continued participation:

- 1) Has there been any change in the subjects' health since their last visit;
- 2) Has subject started or stopped taking any medications since their last visit;
- 3) Has subject taken or applied exclusionary medications (anti-inflammatory, antihistamine, steroid) or made changes in the dosages of reported medications since the previous visit;
If yes, record on CRF CONCOMITANT MEDS and contact the Sponsor
- 4) Has subject used douche products, vaginal medications, suppositories, feminine deodorant spray, powder (in the perineal area), or vaginal wipes for the duration of your study participation; *If yes, record on CRF COMMENTS and contact the Sponsor*
- 5) Has subject refrained from sexual activity for at least 48 hours prior to the examination visit; *If no, record on CRF COMMENTS and contact the Sponsor*
- 6) Has subject only used supplied test products for menstrual protection; *If no, please record on CRF COMMENTS and contact the Sponsor*
- 7) has subject refrained from genital hair removal (e.g. waxing/shaving, etc.)?

3.3 Study Procedures

The complete schedule of study procedures is presented in tabular form in Appendix 1.

Visit 1 (Screening)

Subjects will be initially screened at Visit 1 per the inclusion/exclusion criteria approximately 2 weeks prior to start of subject's menstrual cycle. To determine eligibility, the following will be obtained at the study site:

1. written informed consent;
2. inclusion/exclusion criteria;
3. urine pregnancy test;
4. demographics;
5. medical & gynecological history;
6. medication history;
7. weight and height;

Prior to procedures involving the vulvovaginal area, please complete the following:

8. Ask subject to empty bladder;
9. Have subject disrobe from the waist down and wear a gown or drape sheet;
- 10. Vaginal pH**
11. Speculum insertion;
12. Vaginal assessment (Vaginal Discharge) (Appendix 7);
13. vaginal swabs for Microbiome Assessment (Appendix 9);
14. vaginal exam (Appendix 6);
15. screening STI Microbiology Screening (Appendix 8).

Order of vulvovaginal procedures is:

- **Vaginal pH**
- Vaginal Discharge Assessment
- Vaginal Swabs for Microbiome Assessment
- Vaginal exam
- STI Microbiology Screening (screening visit 1 only)

Following these procedures, the Investigator will determine if the subject has met the initial study eligibility requirements (pending laboratory results). Those subjects who have met the criteria, to this point, will be instructed that they will be notified of their final eligibility to participate in the study after the Investigator has received and reviewed the laboratory results. The subjects who have not met the criteria, at this point, will be informed of their ineligibility to participate and this will end their participation.

Visit 2 (at least one day prior to start of next menstrual cycle)

Subjects who have been found to be eligible to participate will be instructed to return to the study site at Visit 2 and complete the following procedures:

1. medical history update;
2. medication history update;
3. continuance criteria;
4. randomization to study product;
5. provide subjects with instructions, diary and monthly questionnaire, and monthly tampon product (per randomization) to use for their next menstrual cycle (Cycle 1) for the completion of visit. Subjects will also be given a supply of ultra-pads, overnight pads and pantiliners to use a menstrual backup for the provided tampons, if desired;

Visit(s) 3– 5 (within 72 hours after last tampon use)

Subjects will return to the study site at Visit(s) 3-5 and complete the following procedures:

1. medical history update;
2. medication history update;
3. continuance criteria;
4. collect all un-used tampons from prior visit;
5. collect tampon use diary(s);
6. collect monthly post menses questionnaire;

Prior to procedures involving the vulvovaginal area, please complete the following:

7. Ask subject to empty her bladder.
8. Have subject disrobe from the waist down.
9. **Vaginal pH**
10. Speculum insertion
11. vaginal assessment (vaginal discharge) (Appendix 7);
12. vaginal swabs for Microbiome Assessment (Appendix 9)

13. vaginal exam (Appendix 6)
14. AE assessment;
15. provide subjects with instructions, questionnaires (diary and monthly) and monthly tampon product (per randomization) for the completion of visit (Cycle 2-4). Subjects will also be given a supply of ultra-pads, overnight pads and/or pantiliners to use as menstrual backup for the provided tampons, if desired.

Order of vulvovaginal procedures after above has been performed is:

- **Vaginal pH**
- Vaginal Discharge Assessment
- Vaginal Swabs for Microbiome Assessment
- Vaginal exam

Subjects who have abnormalities or irritation identified during their vaginal examination (including vaginal erythema grades ≥ 2.0 and/or abrasions and/or ulcerations which are severe, as determined by the Investigator) may be scheduled for an additional examination at the discretion of the Investigator. Photos maybe taken of the test site area for significant findings at the discretion of the Investigator.

Visit 6 (EXIT: within-72 hour after last tampon use)

Subjects will return to the study site at Visit 6 and complete the following procedures:

1. medical history update;
2. medication history update;
3. continuance criteria;
4. collect all un-used tampons from prior visit;
5. collect tampon use diary(s);
6. collect monthly post menses questionnaire;

Prior to procedures involving the vulvovaginal area, please complete the following:

7. Ask subject to empty her bladder;
8. Have subject disrobe from the waist down and wear a gown or drape sheet;
9. **Vaginal pH**
10. Speculum insertion
11. vaginal assessment (vaginal discharge) (Appendix 7);
12. vaginal swabs for Microbiome Assessment (Appendix 9)

13. vaginal exam (Appendix 6)
14. AE assessment;
15. Subjects has completed the study.

Order of vulvovaginal procedures after above has been performed is:

- **Vaginal pH**
- Vaginal Discharge Assessment
- Vaginal Swabs for Microbiome Assessment
- Vaginal exam

Subjects who have abnormalities or irritation identified during their vaginal examination (including vaginal erythema grades ≥ 2.0 and/or abrasions and/or ulcerations which are severe, as determined by the Investigator) may be scheduled for an additional examination at the discretion of the Investigator. Photos maybe taken of the test site area for significant findings at the discretion of the Investigator. If follow-up is needed, this examination should occur approximately 1 week following Visit 6 and will be used to confirm resolution of the identified abnormalities. At this follow-up visit, if the abnormalities or irritation have not resolved (including erythema grades ≥ 2.0 and/or abrasions and/or ulcerations which are severe, as determined by the Investigator), the Investigator may recommend further medical follow-up for the subject.

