Vaginal Health General Procedures

In General

A physician will conduct all vaginal exams on all subjects at the time points indicated in the Study Events table of the protocol.

At the Screening visit, Vaginal swabs will be collected to rule out positive results Trichomonas, BV and Yeast, Chlamydia, and Gonorrhea (STI).

Supplies:

- Plastic, clear speculums should be used
- Sterile saline
- Appropriate lighting such as a gooseneck lamp or a headlamp; same lighting should be used at all examination intervals
- Aptima Swabs

Vaginal Assessments, Documentation of Findings, and Follow Up PRN

The study Physician of record will conduct the procedures and vaginal exam/assessments appearing below. Any potential confounding activities will also be assessed during the vaginal exam i.e., sexual activity within the past 48 hours or intra-vaginal product use other than study supplied tampons.

All findings either normal and abnormal, will be documented in the eCRF Form, noting score (for erythema) and absence or presence of abrasion, ulceration, laceration, and color and character of vaginal discharge and any evidence of sexually transmitted disease. Document the location, extent, and detailed description of any findings in comments.

Study subjects who have abnormalities or irritation noted on their gynecological examination form may be scheduled for a follow up examination. The Study Physician will determine whether follow-up is necessary. Follow up examinations will occur 1-2 weeks before the start of the subject's next menstrual period.

Procedure Order:

- Subjects will be placed in the dorsal lithotomy position.
- Observe external genitalia and record any findings on eCRF Form;
- A speculum will be inserted into the vagina to visualize the upper 1/3 of the vagina;
- Using the scales and descriptors outlined in the protocol and Appendices, record all findings on eCRF Form;

Appendix 5

ERYTHEMA GRADING SCALE

- 0** No apparent cutaneous involvement.
- 0.5** Greater than 0, less than 1.
- 1** Faint but definite erythema, no eruptions or broken skin or no erythema but definite dryness; may have epidermal fissuring.
- 1.5** Greater than 1, less than 2.
- 2** Moderate erythema, may have a few papules or deep fissures, moderate-to-severe erythema in the cracks.
- 2.5** Greater than 2, less than 3.
- 3** Severe erythema (beet redness), may have generalized papules or moderate-to-severe erythema with slight edema.
- 3.5** Greater than 3, less than 4.

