Appendix 7**Vaginal Assessment****Vaginal pH**

- 1) Use appropriate personal protective equipment.
- 2) Vaginal pH is measured **before** the insertion of a speculum.
- 3) A pH test strip (2.0-9.0 range) is grasped at the end and either held by hand or a sterile hemostat (long tool capable of reaching into the vagina thru the speculum) and carefully brought to the vagina.
- 4) The strip is moistened with the "fluid" from the middle to upper third of the lateral wall of the vagina. It is held in place for 30 sec.
- 5) The strip is carefully removed and the colour change should be "read" immediately after removal.
- 6) The corresponding pH value is recorded on the eCRF Database

Materials

BDH Cat No. 83930.601; gradation in 0.5 units between 2.0 and 9.0.

VAGINAL DISCHARGE:

Discharge: Normal Abnormal

If Abnormal, please indicate color and consistency below:

Color	Consistency
 White	 Red
 Gray	 Green
 Yellow	 Brown
 Other	 Flocculent
	 Frothy
	 Cheesy
	 Other

If Other, please describe:

Evidence of sexually transmitted diseases or other infections? Yes No

If yes, describe:

Appendix 8

STI Microbiology Screening (Visit 1 Only)

Vaginal swab samples will be collected at the screening visit (Visit 1). In keeping with GCP's, subject's specimens will be identified only by their 4-digit subject number.

Aptima swabs will be used for wet mount samples.

All subjects will be screened for the microflora exclusion criteria BV (bacterial vaginosis), *Candida spp.*, *Trichomonas vaginalis*, *Chlamydia trachomatis*, and *Neisseria gonorrhoeae*. The presence of three of the four following criteria is diagnostic of BV: (1) non-viscous homogenous milky Vaginal Discharge, (2) vaginal pH > 4.5, (3) the presence of a fishy amine odor or the production of the odor upon the addition of potassium hydroxide (KOH) to the vaginal discharge, and (4), the presence of clue cells (> 20 % clue cells). All subjects will be tested for *Candida spp.*, *Trichomonas vaginalis*, *Chlamydia trachomatis*, *Neisseria gonorrhoeae* using suitable diagnostic methods. Subjects testing positive for any of the microbial vaginal exclusion criteria will be dismissed from further study participation.

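### Section 3.3 grades the labia minora and introitus only after the pH strip and speculum, whereas Appendix 4 records external genitalia before the speculum; one order should govern

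*Combined protocol and SAP*

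**What the plan says.** Section 3.3 numbers the procedures at each examination visit. At Visits 3-5 and at Visit 6, vaginal pH is step 9, the speculum is step 10 ("10. Speculum insertion"), discharge is step 11, the microbiome swabs are step 12 and the Appendix 6 exam is step 13. Visit 1 runs the same way one number later: pH at step 10, "11. Speculum insertion", then discharge, swabs and the exam at step 14. Each visit also carries a short list confirming that the sequence is intended; for Visits 3-6 it is introduced by "Order of vulvovaginal procedures after above has been performed is". The exam comes after pH, discharge and swabs in each of these lists.

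Appendix 6 has six rows: labia minora, introitus, lower, middle and upper vagina, and cervix. Each is assessed for erythema, abrasion and ulceration. Abrasion and ulceration are Yes/No only. The form has no field for cause.

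Appendix 4, under Procedure Order, starts at the outside: "Observe external genitalia and record any findings on eCRF Form". The next line is "A speculum will be inserted into the vagina to visualize the upper 1/3 of the vagina". A last line then has all findings recorded with the scales.

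Sections 2.1 and 4.4 base the primary conclusion on erythema, ulcerations and abrasions, among other assessments. Section 4.4 plans 95% confidence intervals for the proportions and odds ratios. Exclusion 21 turns away a woman with erythema of grade 2.0 or more or "the presence of abrasions and/or ulcerations as determined by investigator, at the screening visit".

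**The concern.** The labia minora and introitus can be seen without any instrument. In Section 3.3 they are graded only after a strip, a speculum and a swab have passed them. Redness or a superficial abrasion made in those minutes looks the same on the form as one left by the tampon. Neither Appendix 6 nor Section 4.4 separates the two.

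At stake is the absolute level of the erythema and abrasion proportions, which carry the tolerability conclusion, and to a lesser degree the odds ratios. At Visit 1 a mark made during that visit could also decide eligibility. Because Appendix 4 describes a different order for the external genitalia and no section takes precedence, an examiner could follow either and comply with part of the protocol.

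**Working it through.** **1. The orders side by side**

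| Step | Section 3.3, Visits 3-6 | Section 3.3, Visit 1 | Appendix 4 |
|---|---|---|---|
| External genitalia observed and recorded | no separate step | no separate step | before the speculum |
| pH strip | 9 | 10 | not placed |
| Speculum | 10 | 11 | after the external look |
| Discharge | 11 | 12 | not placed |
| Microbiome swabs | 12 | 13 | not placed |
| Graded exam | 13 | 14 | scaled recording listed after the speculum |

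The direct conflict is between the external look and the speculum. Appendix 4 does not name the introitus, does not place the pH strip and does not say when the outer sites receive their scaled score.

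Appendix 9 differs from Section 3.3 as well: it puts the microbiome swab after the visual exam, then has the fornix looked at again and new findings noted. The protocol therefore already allows for findings that first appear during the procedures. It has no such check for the outer sites. The outer-site conflict remains whichever way swab and exam are ordered, because both follow the speculum in Section 3.3.

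**2. Size, for illustration only**

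From the documents: 65 women to complete, four products, one post-use exam per product (Visits 3-6). Assumed, because the documents give no rate: a share q = 1% to 5% of exams leaves a gradable mark on the labia minora or introitus, independently across exams and women.

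- Expected women marked per product, 65 × q: 65 × 0.01 = 0.65; 65 × 0.05 = 3.25.
- Chance of at least one among 65, 1 − (1 − q)^65: 1 − 0.99^65 = 48%; 1 − 0.95^65 = 96%.
- Women with at least one mark over four exams, 1 − (1 − q)^4: 1 − 0.99^4 = 3.9%; 1 − 0.95^4 = 18.5%, so about 4-19%.
- Effect on an absolute rate. The plan names no interval method; with exact (Clopper-Pearson) limits, 0 of 65 gives 0 to 5.5%, and 3 of 65 gives 1.0% to 12.9%. Three procedural marks on a product with no true lesions would move the upper limit by that much.
- Effect on a comparison. Observed rate = p + q − pq, with p the true product rate. Assume p = 5% v 10%, odds ratio (0.10/0.90)/(0.05/0.95) = 2.11. At q = 1% the observed rates are 5.95% and 10.9%, odds ratio 1.93. At q = 5% they are 9.75% and 14.5%, odds ratio 1.57. With equal true rates the odds ratio stays 1.0 at any q.

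The plan has no figure of its own to reproduce here. Section 4.2 bases the 65 on expert judgement and gives no rate.

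**The case against.** The strongest reply is that Appendix 4 and Section 3.3 are closer than they look. A reader might infer that Appendix 4 already orders full grading of the labia minora and introitus before both strip and speculum. It does not: it asks only for external findings to be observed and recorded first, and lists scaled recording after the speculum. That stands, and it limits the direct contradiction to the external look and the speculum.

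Other parts of the reply also carry weight:

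- **Bias between products.** A reader might infer that one product gains. All four are examined in the same written order under blinding, so the documents do not support that. Extra lesions also work against the tolerability claim. With no hypothesis test planned, the shrinkage of odds ratios is secondary.
- **Misattribution is not automatic.** A physician performs every exam and must describe location and extent in comments. The adverse event causality scale allows for a more probable alternative explanation, and acceptance is a medical judgement on a body of evidence. These safeguards help, but Section 4.4 tabulates proportions without a procedural category and does not use the comments to reclassify.
- **Frequency.** The risk assessment in Appendix 2 expects side effects of the examination to be minimal. The documents supply no rate that would show otherwise.
- **Exclusion 21 is narrow.** Faint redness does not exclude; grade 2.0 or an abrasion or ulceration does.
- **Site scope.** Section 4.4 does not say whether labia minora and introitus scores enter the reported proportions. If they do not, the effect on the tables falls away, although the conflict of order remains.

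**Conclusion.** The point holds as a measurement-order problem of modest and unknown size. Section 3.3 has the outer sites graded after instruments have passed them, Appendix 4 has external genitalia recorded before the speculum, and nothing says which governs. Following Section 3.3 as written, an instrument mark at the labia minora or introitus can enter the product's record. It can raise each product's erythema and abrasion proportions, pull odds ratios towards 1 and, at Visit 1, lead to exclusion through an abrasion.

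The conclusion about the text needs no assumption. The effect on the results assumes that outer-site scores enter the tabulated proportions and that instruments sometimes leave a gradable mark there. The figures of 0.65-3.25 of 65 women per product, and 4-19% of women over four exams, rest on an assumed 1-5% rate at those two sites and on independence. They show direction and scale and are not an estimate. A reader might also infer that reordering cleans all the lesion data; it protects two of the six sites.

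**What to change.** In the Section 3.3 lists for Visits 1, 3-5 and 6, make inspection and grading of the labia minora and introitus (the first two rows of Appendix 6) the first vulvovaginal step, before the pH strip and speculum. Grade the vaginal walls, upper vagina and cervix after insertion. Record in comments, as procedural, any outer-site mark first seen after insertion. Amend Appendix 4 to match, naming the introitus, placing the pH strip and saying when the scaled score is given. Settle the swab order in Appendix 9 in the same edit, so that one sequence governs.

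Covering the introitus, and looking before the strip, is a small extension of what Appendix 4 states. Instrument marks at the four internal sites would remain possible.

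The cost is a reordering of lines and one instruction on comments. No visit, procedure or staff is added.
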